In addition to systematically eliciting selected anticipated adverse events as noted above, blinded study coordinators will assess for other unanticipated adverse events at each follow-up contact using the standardized question, “Have there been any changes in your health since your last visit?” Participants will also be given a telephone number that can be used to contact study staff to report any adverse events experienced in between scheduled study visits. Negative changes will be recorded as adverse events on standardized adverse event forms, with documentation of date of onset, date of resolution, likelihood of relationship to treatment, and actions taken in response to the event, and severity according to the CTCAE scale (National Cancer Institute 2009) (see “Safety Assessments” section below).

G.1.4 Demographic and clinical covariates

Structured questionnaires will collect data on the following variables in order to assess eligibility, characterize the study cohort, assess whether groups are comparable at baseline, and guide statistical adjustments in the event that significant differences between groups are detected at baseline:

- A. Sociodemographic history (date of birth, race/ethnicity, education, employment, marital/relationship status);
- B. Medical history (diagnosed medical conditions including coronary disease, diabetes mellitus, hypertension, hypercholesterolemia; use of prescription and OTC drugs);
- C. Reproductive/menopausal history (date of last menstrual period, number of periods in the prior 12 months, hysterectomy, oophorectomy, parity, age of onset of hot flashes, current and past use of hot flash treatments)
- D. Blood and urine testing: Follicle stimulating hormone levels will be measured in women under the age of 60 years with a history of hysterectomy without oophorectomy. Urine pregnancy testing will be performed in women who may still be of child-bearing potential.

G.2 Primary and Secondary Outcomes

- The primary outcome of this trial is *change in the average frequency of any hot flashes* from baseline to 4 and 12 weeks, as documented by symptom diaries.
- Secondary outcomes include changes in frequency of moderate-to-severity hot flashes and total hot flash severity score from baseline to 4 and 12 weeks of treatment, also documented by symptom diaries.

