Headache: Potential side effects of NTG therapy are related to the medication's vasodilatory action. The most commonly reported side effect is headache, occurring most frequently in the first 24 hours of administration (Tfelt-Hansen and Tfelt-Hansen 2009). In previous placebo-controlled trials of intermittent therapy with transdermal NTG (in which the NTG patch was removed at bedtime and replaced the next morning) at 0.2 to 0.8 mg/hr, approximately 60% of participants taking transdermal NTG reported headache, compared to 18% of participants taking placebo (Rossouw, Prentice et al. 2007). Among persons using continuous transdermal nitrate (immediately replacing the old patch with a new patch), development of tolerance to the vasodilatory effects of transdermal nitrate is expected within 12 to 24 hours, which should diminish the frequency and severity of headache. In the study team's prior pilot trial of continuous NTG for treatment of hot flashes in peri- and postmenopausal women, 37% of participants reported headache at some point during the 6-week study but the average duration of headache was less than 24 hours.

Lightheadedness/hypotension: Lightheadedness has been reported with initiation of NTG therapy, presumably due to lowering of blood pressure during the first 12 to 24 hours of administration. In prior placebo-controlled trials of intermittent NTG therapy for other indications, 6% of participants taking transdermal NTG reported transient lightheadedness thought to be associated with lowering of blood pressure, compared to 4% of participants taking placebo (Rossouw, Prentice et al. 2007). It is possible but uncommon for patients using transdermal NTG patches to develop hypotension severe enough to cause syncope. In the case of hypotension, removal of the transdermal patch should result in immediate (within seconds to minutes) normalization of blood pressure. Any lightheadedness or lowering of blood pressure associated with transdermal NTG therapy should

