Study medication may be discontinued if deemed necessary to protect the safety of a participant or preserve the integrity of the study. The decision to discontinue study medication will be made on a case-by-case by the principal investigator, with input from the steering committee and the DSMB as needed. In most cases, discontinuation of study medication will prompt early termination of study participation, although there may be select cases where study medications are discontinued only temporarily, and the participant is subsequently restarted on study medication and then followed for the full duration of the study.

Specific reasons for discontinuation of study medication and/or early termination of the study include: 1) syncopal episode attributable to NTG-induced hypotension or vasodilation; 2) development of persistent blood pressure <90/60, blood pressure <100/60 with symptoms of dizziness, or orthostatic blood pressure with symptoms of dizziness, which do not resolve with reduction in study medication dose; 3) development of persistent severe hypertension defined by blood pressure >180/110; 4) development of pregnancy or decision to try to become pregnant (among women who are not yet postmenopausal); 5) development of another clinically significant adverse event limiting a participant's ability to safely continue to use the study drug; 6) unusually disruptive behavior exhibited by a participant during study visits that endangers the safety or well-being of the participant or study staff; or 7) decision to terminate the study by the IRB, the NIA, or other regulatory bodies.

Participants may also withdraw voluntarily from participation in the study at any time and for any reason. If a participant decides to discontinue the study drug or withdraw from the study, the study coordinator will try to elicit the reason for this decision. The coordinator may also try to trouble-shoot participant concerns or discuss strategies for overcoming barriers to continued participation in the study in order to try to retain the participant, provided that the decision to terminate is not driven by a safety issue.

J.2 Discontinuation/Termination Procedures

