In the event that study medication is discontinued early, study coordinators will attempt to schedule an early termination visit to collect outcomes data, provided that the participant is willing, and provided that the principal investigator (with input from the steering committee and DSMB as appropriate) judges that it is safe and feasible to do so.

This visit will include as many of the procedures originally scheduled to take place at the 12-Week Clinic Visit as possible, such as: completion of a final hot flash diary; assessment of adverse events; re-administration of other symptom and quality-of-life questionnaires; review of current medications; re-assessment of weight, blood pressure, and heart rate; and administration of a satisfaction questionnaire.

Regardless of whether the participant is able to complete an early termination visit, the study coordinator will document the reason for early termination in the participant's file, except in cases where a participant is lost to follow-up or declines to provide a reason for deciding to discontinuing participant early.

Upon study termination, participants will be asked to wean off NTG (or placebo) over the next 1 to 3 days, by decreasing their patch dose on a nightly basis before stopping NTG/placebo completely. Specifically, participants who are being weaned from the 0.6 mg dose of study medication will be instructed to switch to 0.4 mg for one day, then to 0.2 mg for one day, then to stop study drug altogether. Participants who are being weaned from the 0.4 mg dose will switch to 0.2 mg for one day before stopping medication altogether. Women who are taking the 0.2 mg (the lowest dose hypothesized to have a therapeutic effect) will simply stop study medication without any change in dose. Participant and staff blinding will be maintained throughout the weaning process; for participants taking placebo, weaning will use placebo rather than active NTG patches. If necessary, women will be given a last supply of NTG or placebo medication (one patch of each dose strength needed to complete the weaning).

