headache during the first 24 hours of therapy, but no significant differences in rates of chest pain, syncope, or severe adverse events defined by CTCAE severity grade 3 or higher.

K.2 Data Analyses

K.2.1 Analyses for Objective 1

Analyses to address aim 1 will examine change in average daily hot flash frequency from baseline to 4 and 12 weeks of treatment, measured over 7 days by validated hot flash diaries (Sloan, Loprinzi et al. 2001, Food and Drug Administration 2003). The effect of NTG therapy will be estimated using linear mixed models (LMMs) for the repeated changes, adjusting for baseline values, under the assumption of an approximately constant treatment effects at 4 and 12 weeks; in supplementary analysis we will assess evidence for differences in the treatment effects at these two time points. The distribution of the LMM residuals will be assessed using Q-Q plots, and outcomes will be transformed if necessary to achieve approximate normality. Analyses will be by intention to treat, according to treatment assignment, and without regard to adherence.

K.2.2 Analyses for Objective 2

For additional confirmation of treatment effects on frequency of any hot flashes, we will also assess treatment effects on moderate-to-severe hot flashes and on total hot flash severity scores as secondary outcomes, also assessed by diary, using the same methods. The distribution of the LMM residuals will again be assessed using Q-Q plots, and outcomes will be transformed if necessary to achieve approximate normality. Analyses will again be by intention to treat, according to treatment assignment, and without regard to adherence.

K.2.3 Analyses for Objective 3

Analyses to address aim 2 will examine changes in sleep quality and duration, anxiety and depressive symptoms, and menopausal quality-of-life from baseline to 4 and 12 weeks. These outcomes will be captured by scores on validated self-administered questionnaires, with supplementation by sleep diary in the case of sleep duration. Intervention effects on these outcomes will be estimated using LMMs, adjusted for baseline scores. Approximate normality of the residuals will be checked using Q-Q plots, and outcomes will be transformed if necessary. Analyses will once again be by intention to treat and without regard to adherence.

K.2.4 Analyses for Objective 4

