Under these assumptions, a sample size of 140 (70 per group) should provide an estimated 87% power in 2-sided tests with type-I error of 5% to detect an 20% greater reduction in hot flash frequency (or 1.8 hot flashes per day) in the active treatment arm relative to the control arm. This will correspond to a 50-55% decrease in hot flash frequency from baseline in the active treatment group, which has previously been described as a clinically important effect in prior hot flash research (Butt, Deng et al. 2007). Estimates account for correlation of the repeated measures and loss to follow-up of up to 15%, and indicate that power will remain $\geq 80\%$ even if actual effect size or other parameters are less favorable than expected. This sample of 70 per group will also provide $>80\%$ power in 2-sided tests with type-I error of 5% to detect a between-group difference in mean frequency of moderate-to-severe hot flashes of ~ 1.5 hot flashes per day, as well as ~ 3.3 points in hot flash severity scores.

K.4 Additional Statistical Considerations

K.4.1 Drop-out rates

Based on past experience, participant dropout levels are expected to remain under 15% over 12 weeks. The assumption of non-informative dropout will be examined by comparing the baseline characteristics and early post-randomization outcomes of participants who are lost to follow-up versus retained in the study. If drop-out rates differ substantially between groups, analyses will be adjusted for baseline covariates associated with retention. In sensitivity analyses, we will also use multiple imputation of missing outcomes under plausible informative missingness assumptions, along with standard methods for calculating summary estimates and confidence intervals, to assess the potential impact of loss to follow-up on treatment effect estimates (Schafer 1999).

K.4.2 Dose effects

In the event that an overall treatment benefit is detected over 12 weeks, we will conduct exploratory analyses to probe for differences in the magnitude of treatment effects by highest-achieved NTG dose, by testing for interaction between treatment assignment and highest-achieved NTG dose in a linear mixed model for change in hot flash frequency. This analysis will control for the main effect of highest achieved dose to control the placebo effect of this self-selected variable, as well as baseline factors that may confound it, such as age, body mass index, and baseline hot flash frequency or severity.

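### Section K.4.1 ties covariate adjustment for drop-out to unequal drop-out rates, which is the wrong trigger; a short covariate set fixed in advance would close a limited gap at little cost

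*Combined protocol and SAP*

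**What the plan says.** The rule is in K.4.1: "If drop-out rates differ substantially between groups, analyses will be adjusted for baseline covariates associated with retention". The section does not say how large a difference counts, which covariates are candidates, how association with retention is judged, or whether the adjusted model replaces the primary one.

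The primary analysis in K.2.1 uses "linear mixed models (LMMs) for the repeated changes, adjusting for baseline values". No other covariate is named, although H.1.4 stratifies randomization by menopausal stage. G.1.4 adds a second data-dependent route: covariates are collected partly to "guide statistical adjustments in the event that significant differences between groups are detected at baseline".

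Two steps in K.4.1 do not depend on the trigger. Non-informative drop-out is examined by "comparing the baseline characteristics and early post-randomization outcomes of participants who are lost to follow-up versus retained in the study"; neither a comparison by arm nor a resulting action is stated. The section then says: "In sensitivity analyses, we will also use multiple imputation of missing outcomes under plausible informative missingness assumptions". The scenarios are not given.

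On follow-up, J.1 says: "In most cases, discontinuation of study medication will prompt early termination of study participation". J.2 softens this, because "study coordinators will attempt to schedule an early termination visit to collect outcomes data".

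**The concern.** Bias from drop-out depends on who leaves each arm and how they would have fared, not on whether the two percentages match. If women with a given prognostic characteristic tend to leave one arm and stay in the other, the retained groups are no longer comparable even when 15% leave each. The rule then takes no action. The pooled comparison of lost with retained women can miss it too, because opposite patterns in the two arms cancel.

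The timing of the diaries makes early loss the sensitive case. The first on-treatment diary covers the week before the 5-week visit (G.1.1), after the dose increases at weeks 1 and 2 (F.1.6). A woman lost before then gives the mixed model no scheduled outcome. In the pilot, 2 of 19 women stopped for headache before the first outcome assessment (C.3).

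The second issue is pre-specification. Nothing requires the choice of covariates to be settled before the treatment effect can be seen.

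**Working it through.** **1. The plan's own power figure.** Inputs from K.3: SD of change 4.5, baseline/follow-up correlation 0.55, effect 1.8, two-sided 5%, 70 per arm with 15% loss, so 70 × 0.85 = 59.5 per arm. The correlation r between the two follow-up diaries is not given and is assumed.

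- Single-visit variance: 4.5² / (2 × (1 − 0.55)) = 22.5.
- Residual variance of the baseline-adjusted mean of two visits: 22.5 × ((1 + r)/2 − 0.55²).
- r = 0.50: variance 10.07, SD 3.17, standard error 3.17 × √(2/59.5) = 0.582, 1.8/0.582 = 3.09, power 87.2%.
- r = 0.55: variance 10.63, SD 3.26, standard error 0.598, power 85.3%.
- Over r = 0.45 to 0.70, power runs from 89.0% to 79.9%.

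The stated 87% is reproduced and is not in dispute.

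**2. How the trigger behaves at 70 per arm**, under three readings of the undefined threshold:

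| True drop-out | Fisher p < 0.05 | Gap ≥ 10 points | Gap ≥ 5 points |
|---|---|---|---|
| 15% vs 15% | 3.0% | 12.3% | 40.6% |
| 10% vs 20% | 30.5% | 54.7% | 80.5% |

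So whether covariates enter depends heavily on a definition the plan does not give.

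**3. Bias with equal rates.** The planned two-visit model was simulated with 70 per arm, no treatment effect, r = 0.55, 2,000 replicates and about 14.5% loss in each arm. Assumptions: the factor driving loss acts in opposite directions in the two arms, with log-odds 1.0 per SD (odds ratio 2.7). Where the driver is a baseline covariate X, X is worth 1.5 flashes/day per SD. The Monte Carlo error of each bias is 0.013. The sign follows from the assumed direction and could be reversed.

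| Driver of loss | Bias, baseline value only | Bias, X added |
|---|---|---|
| X, lost before 5 weeks | −0.39 | 0.00 |
| X, lost after 5 weeks | −0.10 | 0.01 |
| Baseline frequency | 0.00 | −0.01 |
| Observed 5-week diary | −0.01 | −0.01 |
| Unobserved 12-week value, lost after 5 weeks | −0.34 | −0.31 |
| Unobserved 12-week value, lost before 5 weeks | −0.61 | −0.49 |

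As fractions of the planned effect, 0.39/1.8 = 22% and 0.10/1.8 = 6%. In the first row, type I error is 10.7% without X and 5.4% with it.

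**4. Hand check of the first row.** For a standard normal X and logistic drop-out probability π with slope k and mean p, the mean of X among retained women shifts by k × E[π(1 − π)] / (1 − p). With k = 1 and p = 0.144, E[π(1 − π)] = 0.109, so the shift is 0.109/0.856 = 0.128 per arm. Opposite slopes give bias 2 × 0.128 × 1.5 = 0.38, in line with 0.39. The same formula gives 0.17 at k = 0.5 (simulated 0.19, loss 11.8%) and 0.61 at k = 1.5 (simulated 0.61, loss 17.8%). Selection in one arm only halves the bias.

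**5. Cost of always adjusting** (r = 0.55, 59.5 per arm, t-based). Power is 84.8% with no added covariates. Three added terms (menopausal stage, age, body mass index) give 83.8% if useless, 85.6% if they explain 5% of residual variance and 87.4% if 10%. Five useless terms give 83.1%, a loss of 1.7 points.

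**6. Freedom to choose the model.** With completely random loss (4,000 replicates, normal reference distribution), type I error was 6.2% for the baseline-only model, 6.3% when the rule was applied mechanically with a 5-point gap, and 7.4% when the better of two models was reported. A fixed six-covariate model gave 7.05% in the same run. Much of the 7.4% may therefore come from using a normal rather than a t reference, and this run does not isolate a selection effect.

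**The case against.** The strongest reply is that K.4.1 does not stand alone. The mixed model keeps the 5-week diary of women lost later, and the baseline value covers loss driven by symptom frequency; the simulation supports both. The imputation is unconditional, and early termination visits may recover some diaries. All of this stands. A reader might infer that drop-out bias goes unaddressed whenever the rates match, and the documents do not support that. The limits are that the imputation is a sensitivity analysis with unstated scenarios, and that it does not alter the primary estimate.

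A second reply concerns mechanism. It is tempting to argue that women on NTG will leave for headache and women on placebo for lack of effect, citing I.1.1, where "approximately 60% of participants taking transdermal NTG reported headache, compared to 18% of participants taking placebo". That figure comes from intermittent therapy. The same section expects less headache with continuous use and reports 37% in the pilot, lasting under 24 hours on average. The run-in also removes some sensitive women, though only at 0.1 mg/hr, below every randomized dose. More important, headache and lack of effect arise after randomization, and lack of effect is the outcome itself. Baseline covariates would not cure such loss, as the last two rows of the table in step 3 show. The documents also do not show that age, body mass index or menopausal stage drives loss in opposite directions.

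Third, the assumed selection is strong. In a simpler comparison of completers, which is not the planned analysis, odds ratios of 2.7 to 4.5 with outcome correlations of 0.3 to 0.4 give 0.26 to 0.46 flashes/day, but an odds ratio of 1.5 with correlation 0.2 gives only 0.08.

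Fourth, the rule looks at retention rather than efficacy, and applied mechanically it left type I error unchanged. A reader might infer that the primary model will be picked for its result. The text leaves room for that but does not say it.

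**Conclusion.** The point holds in limited form. The rate-based trigger is the wrong criterion, and without a threshold or covariate list it leaves the primary model unsettled until retention is known. The uncovered gap is loss driven by prognostic baseline factors other than hot flash frequency, mainly before the 5-week diary. About 0.1 to 0.4 flashes/day is an illustration resting on opposite selection at an odds ratio of 2.7 per SD, a covariate worth 1.5 flashes/day per SD, and about 14.5% loss per arm. None of the selection strengths comes from the documents, so this is not a forecast. Loss related to unobserved outcomes is a separate problem, which only the imputation can address. The case for change rests on the weak rule and its cheap replacement, not on a demonstrated large bias or an inflated error rate.

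**What to change.** Delete the rate-based trigger in K.4.1. State in K.2.1 that the primary mixed model always includes baseline frequency, menopausal stage, age and body mass index. Baseline frequency is already in the model, menopausal stage is the randomization stratum and is now absent, and all four are already collected. State also that no test of baseline differences under G.1.4 will alter this model.

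Extend the K.4.1 check so that predictors of loss and reasons for loss are compared by arm. Keep the planned imputation, but write down its scenarios, allowing different departures in each arm, before unblinding.

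The cost is wording and three extra model terms: about 1 point of power if they are useless (84.8% to 83.8%), and a gain if they explain 5% of residual variance. No new data are needed. The adjustment will not remove bias from loss driven by unobserved outcomes, and the plan should say so.

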APPENDIX A: Summary of Measures and Procedures at Study Visits

| Measures | Telephone Screening | Screening Clinic Visit | Run-in period | Baseline Clinic Visit | 1-Week Clinic Visit | 2-Week Clinic Visit | 3-Week Phone Call (for 0.6 mg) | 5-week Clinic visit | 8-Week Phone Call | 12-Week clinic Visit | 4-Week Post-Discontinuation Phone Call |
|---|---------------------|------------------------|---------------|-----------------------|---------------------|---------------------|--------------------------------|---------------------|-------------------|----------------------|--|
| Brief telephone eligibility survey | X | | | | | | | | | | |
| Informed consent documentation | | X | | | | | | | | | |
| Sociodemographics questionnaire | | X | | | | | | | | | |
| Medical/reproductive history questionnaire | | X | | | | | | | | | |
| Blood and Urine Testing | | X | | | | | | | | | |
| Electrocardiography | | X | | | | | | | | | |
| Current medications inventory | | X | | | | | | | | | |
| Alcohol and tobacco use questionnaire | | X | | | | | | | | | |
| Height and weight measurement | | X | | | | | | | | X | |
| Resing blood pressure & heart rate | | X | | X | X | X | | X | | X | |
| Orthostatic blood pressure and heart rate | | X | | X | X | X | | X | | X | |
| 0.1 mg/hr NTG patch run-in period | | | X | | | | | | | | |
| Hot flash symptom diary return | | | | X | | | | X | | X | |
| Pittsburgh Sleep Diary | | X | | X | | | | X | | X | |
| Randomization to NTG or placebo | | | | X | | | | | | | |
| Review of adherence to patches | | | | X | X | X | X | X | X | X | |
| Patch dose escalation | | | | | X | X | | | | | |
| Weaning of NTG or placebo patches | | | | | | | | | | X | |
| Hot Flash Related Daily Interference Scale | | X | | | | | | X | | X | |
| Pittsburgh Sleep Quality Index | | X | | | | | | X | | X | |
| Menopause-specific Quality of Life | | X | | | | | | X | | X | |
| Generalized Anxiety Disorder – 7 | | X | | | | | | X | | X | |
| Center for Epidemiologic Studies Depression | | X | | | | | | X | | X | |
| Adverse events assessment | | | | X | X | X | X | X | X | X | X |

REFERENCES CITED

Avis, N. E., S. L. Crawford, G. Greendale, J. T. Bromberger, S. A. Everson-Rose, E. B. Gold, R. Hess, H. Joffe, H. M. Kravitz, P. G. Tepper and R. C. Thurston (2015). "Duration of menopausal vasomotor symptoms over the menopause transition." *JAMA Intern Med* **175**(4): 531-539.

